## 16. EFFICACY OUTCOMES

### 16.1. PRIMARY EFFICACY

#### 16.1.1. PRIMARY EFFICACY VARIABLE & DERIVATION

The primary efficacy variable is the percent of subjects achieving a 50% or greater reduction in CS dose (prednisone or equivalent) at Week 39 (Visit 14) from Baseline/Week 0 (Visit 1).

The prescribed CS dose (mg) is reported under item 3 on the CS Use page of the eCRF. Prednisone equivalent dose is also collected on the eCRF if prednisone is not the prescribed CS. The prednisone dose (if prednisone is the prescribed CS) or prednisone-equivalent dose (if prednisone is not the prescribed CS) will be used for primary analysis. The frequency of prescribed dose (Item 4) is reported as either "total daily" or "every other day". For analyses "every other day" doses will be normalized to daily doses as described in the protocol ( $[\text{every other day dose}]/2 = \text{daily dose}$ ). All CS use data will be presented in a listing.

At each scheduled visit, a subject was to enter all prescribed CS doses that were in effect since the date of the last scheduled visit up to the date of the current scheduled visit on the CS Use page of the eCRF, including all changes to the prescribed CS doses that occurred during this time period. In some instances an unscheduled visit could have been used to document changes to the prescribed CS doses.

The average daily CS dose will be derived for each subject at each scheduled visit as follows based on the prescribed dose and the time interval taking into account any prescribed dose changes between routinely scheduled visits entered as either Unscheduled Visits or as Add Entry fields under the routinely scheduled visits:

- For each scheduled visit, define the time period for deriving the average daily CS dose at the current scheduled visit as follows: from the date of the last scheduled visit + 1 to the date of the current scheduled visit, inclusive. For example, for Week 39, the time period would be from the day after the date of visit for Week 36 to the date of visit for Week 39, inclusive. For the purpose of deriving the primary efficacy variable, Baseline and ET visits are also considered scheduled visits. Note a subject may have one or two Early Termination visits. The time periods for these visits are defined as follows:
  - Baseline Visit: from the day after the date of visit for Week -3 to the date of visit for Week 0, inclusive.
  - Early Termination Visit 1: from the day after the date of the last scheduled visit to the date of visit for the Early Termination Visit 1, inclusive.
  - Early Termination Visit 2 (if performed): from the day after the date of the Early Termination Visit 1 to the date of visit for the Early Termination Visit 2, inclusive.

Document: CCI

Author: PPD

Version Number:

Version Date:

Final 2.0  
12Apr2019

Template No: CCI

Effective Date: 01Apr2016

Reference: CCI

Copyright © 2009, 2010, 2012, 2016 CCI. All rights reserved.

The contents of this document are confidential and proprietary to CCI. Unauthorized use, disclosure or reproduction is strictly prohibited.

## Analysis Plan

- Calculate the total CS dose for each distinctive CS dose regimen in effect during this time period:
  - If the frequency is “total daily” for the CS dose regimen, then total CS dose = daily CS dose x number of days this CS dose regimen in effect
  - If the frequency is “every other day” for the CS dose regimen, then total CS dose = (every other day CS dose / 2) x number of days this CS dose regimen in effect
- Calculate the total CS dose for the time period as the sum of the total CS doses for all distinctive CS dose regimens in effect during this time period.
- Calculate the average daily CS dose: Average daily CS dose = Total CS dose / (date of current scheduled visit – date of last scheduled visit)

The calculated average daily CS dose at the scheduled visits will be used in all relevant efficacy analyses.

Note, as stated above, in general the average daily CS dose will only be derived at the scheduled visits, which include early termination visit(s). Unscheduled visits, if any, typically will fall between two scheduled visits and hence any prescribed CS dose data at unscheduled visits will automatically be taken into consideration in the algorithm above.

The only exception to this rule will be when a subject has an unscheduled visit AFTER the last scheduled visit and prescribed CS dose data were captured at this last unscheduled visit. For example, there may be rare occasions when a subject withdrew early from the study but did not return for any early termination visits; however, it was known that the subject’s prescribed CS dose increased after the last scheduled visit and such dose increases were captured using an unscheduled visit. In this case the average daily CS dose will be additionally derived at the last unscheduled visit, and the time period for this visit will be: from the day after the last scheduled visit to the date of visit for the last unscheduled visit, inclusive.

The derived average daily CS dose at an unscheduled visit after the last scheduled visit will not be used directly in any summary tables that use scheduled visits but will be eligible for the LOCF/WOCF algorithm. This approach is deemed to be conservative should such an unscheduled visit capture an increase in CS dose.

Missing either the prescribed dose or the frequency of the dose for at least 1 CS dosing record at a visit will lead to missing derived average daily dose.

The percent change in daily CS (prednisone or equivalent) dose (%) will be calculated as:

- $$\frac{[\text{Average daily dose at a postbaseline visit} - \text{Average daily dose at baseline}]}{[\text{Average daily dose at baseline}]} \times 100$$

The percentage of subjects achieving a 50% or greater reduction in CS dose at Week 39 will be calculated for each treatment group.

Document: CCI

Author: PPD

Version Number:

Version Date:

Final 2.0

12Apr2019

Template No: CCI

Effective Date: 01Apr2016

Reference: CCI

Copyright © 2009, 2010, 2012, 2016 CCI. All rights reserved.

The contents of this document are confidential and proprietary to CCI. Unauthorized use, disclosure or reproduction is strictly prohibited.

**16.1.2. MISSING DATA METHODS FOR PRIMARY EFFICACY VARIABLE**

Subjects who discontinued the study early with adverse outcomes related to MG will be considered as not achieving a 50% or greater reduction. The missing dose reduction at Week 39 will be imputed using the WOCF method.

For subjects who do not have CS dose prescribed at Week 39 due to other reasons, the LOCF will be used to impute the prescribed CS dose at Week 39. The last non-missing post-baseline value (including scheduled, unscheduled, and early termination) prior to Week 39 will be carried forward to determine whether a subject achieves a 50% or greater reduction at Week 39. Subjects with no post-baseline CS dose will be excluded from analysis.

Refer to section 16.1.4 for analyses on sensitivity to missing data.

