3.4.3 Method of Assigning Subjects to Treatment Groups

This is a randomized, double-blind, placebo-controlled study; subjects will be randomized in a 1:1 ratio via Interactive Web Response System (IWRS) into IGIV-C treatment group and Placebo treatment group to receive either IGIV-C or matching Placebo every three weeks in a double-blind fashion via IV administration. Each subject's IGIV-C dose will be individualized based on the subject's body weight and the protocol specified loading dose of 2 g/kg over 2 consecutive days and maintenance dosage of 1 g/kg over 1 day every three weeks through Visit 13 (Week 36). Therefore, each subject's infusion volume and duration of the infusion will vary from subject to subject, and must be carefully prepared by the unblinded pharmacist who will prepare IP consisting of either IGIV-C or an equivalent volume of 0.9% sodium chloride injection. Note that for the loading dosage, 2 days is standard (2-4 days is allowed as an extension for tolerability issues or higher weight, i.e., limit for IGIV-C infusion is no more than 80 g/day [corresponding to 80 kg body weight]). Similarly, the maintenance dosage is given over 1 day as the standard time interval (divided dosage over 2 days is allowed for tolerability issues or higher weight, i.e., limit for IGIV-C infusion is no more than 80 g/day [corresponding to 80 kg body weight]).

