5 STATISTICAL METHODS AND DETERMINATION OF SAMPLE SIZE

5.1 Statistical and Analytical Plan

Unless otherwise specified, descriptive statistics will include the number of non-missing observations, mean, standard deviation (SD), median, minimum, and maximum values for the continuous/quantitative data or absolute and relative frequency counts and percentages for categorical/qualitative data. All inferential tests are two-sided with alpha level at 0.05.

Data handling and evaluation procedures will be described in the Statistical Analysis Plan.

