5.2 Determination of Sample Size

In order to provide 80% power to detect a 40% treatment difference (70% IGIV-C versus 30% Placebo group) in the percent of subjects achieving a 50% or greater reduction in CS dosage at Week 39, alpha level = 0.05, a minimum of 24 subjects per treatment group is required. Assuming a discontinuation rate in the range of 20%, 60 subjects are planned to be randomized for the study. This is necessary to accommodate attrition anticipated.

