**Analysis Plan**

the closest previous non-missing value. Note that if a subject has missing values immediately after baseline, the baseline observation will not be carried forward and these values will be left as missing, with the exception of the primary efficacy variable of CS dose, for which the baseline value is eligible for the WOCF algorithm only.

For the same efficacy endpoints above that utilize the LOCF/WOCF algorithm, separate analyses will also be performed using observed data only without imputing any missing data. This non-imputation method will be referred to as the OC.

Missing values for the binary endpoints (e.g., whether or not the subject experienced CS dose reduction) will be handled similarly as for the continuous endpoints. First, the LOCF/WOCF algorithm above will be used to impute the (continuous) missing values. The imputed values will then be used to derive the binary endpoints. The binary endpoints will also be analyzed with the OC approach.

Efficacy analyses will be performed on the mITT population using both the LOCF/WOCF and OC approaches with regards to the missing data, which should allow for more robust assessments of efficacy. See Section 16 for the set of analyses using each of the two approaches. The LOCF/WOCF endpoint row in by-visit listings will indicate the value that was used in the LOCF/WOCF efficacy analysis.

The total scores of QMG, MG Composite, MG-QOL 15, MG-ADL and World Health Organization – Five Well Being Index (WHO-5; see Section 16.3.1.14) are calculated and reported in the eCRF. If one or more items are missing at a given assessment, the total score will be set to missing.

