**16.1.3. PRIMARY ANALYSIS OF PRIMARY EFFICACY VARIABLE**

The primary objective of this study is to test the null hypothesis that the percent of subjects achieving a 50% or greater reduction in CS dose at Week 39 from Baseline in the IGIV-C group is equal to the percent in the Placebo group ( $P_1=P_2$ ). The alternative hypothesis is that the percent of subjects achieving a 50% or greater CS dose reduction in the IGIV-C group is not equal to the percent in the Placebo group ( $P_1 \neq P_2$ ).

The treatment comparison will be analyzed using Cochran-Mantel-Haenszel (CMH) test (Mantel, 1963), adjusted for baseline CS dose level (15-40 mg versus 41-60 mg). The p-value will be based on the general association statistic. The odds ratios for each baseline dose level, the common odds ratio and the Breslow-Day test for homogeneity of the odds ratios will be also summarized.

In the case of sparse events, where at least one of the frequencies is less than 5 in a given cell (i.e., a unique combination of baseline CS dose level, treatment, and the binary response), both unstratified and stratified analyses will be performed using exact methods. For the unstratified analysis, the Fisher's exact test (Agresti, 1992) will be used for treatment comparison. The odds ratio and the exact 95% confidence interval will also be calculated overall and separately for each stratified baseline CS dose level (15-40 mg/day versus 41-60 mg/day). For the stratified analysis, the Zelen's exact test will be used to test homogeneity of odds ratios. The CMH common odds ratio and its exact 95% confidence interval will also be calculated. Finally, an exact test will be used to test the hypothesis of the common odds ratio being 1.

The primary efficacy analysis will be performed for the mITT population.

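### SAP 16.1.2 drops dosed subjects with no derivable post-baseline CS dose, although one early recorded dose would make the same subject a non-responder

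*SAP*

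**What the plan says.** SAP 5.3 defines the mITT set as subjects randomised and given at least one dose of study medication. SAP 16.1.3 says: "The primary efficacy analysis will be performed for the mITT population".

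SAP 16.1.2 sets two branches for a missing Week 39 dose.
- **WOCF branch:** subjects who discontinue with MG-related adverse outcomes (criteria in SAP 7.3) count as non-responders, imputed by WOCF.
- **LOCF branch:** for all others the last post-baseline value is carried forward, whether from a scheduled, unscheduled or early termination visit. The section then ends this rule with "Subjects with no post-baseline CS dose will be excluded from analysis".

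SAP 7.3 agrees for values missing straight after baseline: "the baseline observation will not be carried forward and these values will be left as missing". It goes on to make one exception: for CS dose, baseline is eligible for WOCF. The exclusion sentence in 16.1.2 does not repeat that exception.

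SAP 16.1.1 treats early termination visits as scheduled visits for the dose derivation. It also derives a dose at a last unscheduled visit that falls after the last scheduled one. An incomplete dosing record (dose or frequency missing) makes the derived average missing.

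Protocol 5.1.3.1 has LOCF for early leavers without MG worsening and states no such exclusion. SAP 3.3 lists one change from the protocol, ITT to mITT.

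**The concern.** Two dosed subjects who stop equally early, on the same unchanged CS dose, are handled differently. If one post-baseline dose was recorded, the subject stays in the denominator as a non-responder. If none was recorded, the subject leaves the denominator. What separates them is whether a record exists, not their CS outcome.

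The set analysed is then not the set declared, and SAP 3.3 does not list this second narrowing. With about 30 subjects per arm, each deletion moves the response rate of its arm upwards, so unequal deletions distort the treatment difference.

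**Working it through.** **Inputs**
- Test level: "All inferential tests are two-sided with alpha level at 0.05" (Protocol 5.1).
- Planning rates: 70% IGIV-C, 30% placebo, 80% power (Protocol 5.2).
- Size: "a minimum of 24 subjects per treatment group is required" and "Assuming a discontinuation rate in the range of 20%, 60 subjects are planned to be randomized for the study" (Protocol 5.2).
- Allocation: 1:1 (Protocol 3.4.3), so 60/2 = 30 per arm.
- Assumption: all 30 per arm are treated, and k of them have no derivable post-baseline CS dose, with k = 0 to 3. The documents give no value for k.

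**1. The plan's own figure.** With pooled variance under the null,
n = [1.96·√(2·0.5·0.5) + 0.842·√(0.7·0.3 + 0.3·0.7)]² / 0.4² = (1.386 + 0.545)² / 0.16 ≈ 23.3, so 24 per arm. Then 48/(1 − 0.20) = 60. Both stated figures reproduce.

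**2. When can LOCF first give a response?** Protocol 3.3.1 keeps CS stable in run-in. The first taper step follows the Week 9 infusion, and each visit's average covers the interval since the previous visit. The averages at Weeks 3, 6 and 9 therefore equal baseline. Following Protocol Table 3-1 without worsening:
- Baseline 20 mg/day: 15 at Week 12 and 10 at Week 15. The 50% mark is first met at Week 15 (the same visit for 15 mg/day).
- Baseline 30: 25, 20, 15. First met at Week 18 (the same for 25).
- Baseline 60: 50, 40, 35, 30. First met at Week 21 (the same for 40 and 50).

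On the protocol schedule, a value carried from Week 3, 6 or 9 is always a non-response.

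**3. Who is actually dropped?** Only an mITT subject on the LOCF branch with no CS dose at any post-baseline scheduled, early termination or last unscheduled visit, or whose records are too incomplete to derive one.

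**4. Do the sensitivity analyses restore them?** No. SAP 16.1.4 plans a PP analysis under the same rules and an observed-case analysis that excludes anyone without a Week 39 dose.

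**5. Effect on the estimate.** Counted as non-responders, the result is 21/30 − 9/30 = 70.0% − 30.0% = 40.0 points. If k non-responders are excluded from one arm:

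| k | IGIV-C only: 21/(30−k) − 9/30 | Placebo only: 21/30 − 9/(30−k) |
|---|---|---|
| 1 | 72.4 − 30.0 = 42.4 | 70.0 − 31.0 = 39.0 |
| 2 | 75.0 − 30.0 = 45.0 | 70.0 − 32.1 = 37.9 |
| 3 | 77.8 − 30.0 = 47.8 | 70.0 − 33.3 = 36.7 |

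**6. Effect near the threshold.** These are unstratified two-sided Fisher p-values, for illustration. SAP 16.1.3 uses a stratified CMH test, with exact methods when a cell count is below 5, and stratum counts are not available.
- 17/30 versus 9/30: p = 0.067. Excluding one IGIV-C non-responder, 17/29 versus 9/30: p = 0.037.
- 18/30 versus 9/30: p = 0.037. Excluding three placebo non-responders, 18/30 versus 9/27: p = 0.064.
- At the planning rates, 21/30 versus 9/30: p = 0.0041. Excluding two IGIV-C subjects: p = 0.0008. The conclusion does not change.

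**7. Power under a non-responder rule.** Same formula as step 1, with 70%/30% among the remaining subjects. If k are missing in both arms, power is 87.0%, 84.4% and 81.7% for k = 1, 2, 3 (88.2%, 87.0% and 85.7% if excluded). If they are missing on IGIV-C only, it is 85.0%, 79.8% and 73.8%.

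**The case against.** The strongest reply is that hardly anyone meets the rule. Protocol 3.11 asks every dosed early leaver to attend an Early Discontinuation Visit, at which the CS dose is recorded. It also asks for visits 6 and 9 weeks after the last infusion. SAP 6.4 and 16.1.1 feed such data into the derivation. A reader might infer that anyone who leaves before Week 3 is deleted. The documents do not support that: a subject leaving at Week 2 with a valid record at any of these contacts stays in, normally as a non-responder. Subjects who discontinue with MG-related adverse outcomes also stay in, through WOCF.

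A reader might also infer that the rule favours IGIV-C, because early infusion intolerance is likelier on active drug. That is plausible but not documented. No early discontinuation rate by arm is given, infusions may be slowed, and placebo losses work the other way.

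Finally, this is a Phase 2 proof-of-concept study, the p-value crossings above use chosen counts, and the move from ITT to mITT is openly declared.

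All of this limits the size of the problem, and all of it stands. It does not remove the inconsistency for the remaining subjects. The discontinuation visit depends on the subject's willingness, and an incomplete record has the same effect as none.

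**Conclusion.** The point holds, as a narrow and cheaply corrected inconsistency. For mITT subjects on the LOCF branch with no derivable post-baseline CS dose, deletion conflicts with the declared population and with the outcome that LOCF assigns after one early recorded dose. No planned analysis shows its effect.

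On the assumed 0 to 3 subjects per arm, all losses in one arm and 30 treated per arm, the estimated difference moves by −3.3 to +7.8 points around 40.0. With none affected it does not move. At the planning rates the conclusion is not at risk. In a result near 0.05, one subject could decide it.

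Two stronger conclusions do not follow. The rule is not shown to favour IGIV-C, and a non-responder rule could make the result more favourable as well as less. Whether to repeat the analysis on the protocol's ITT set is a separate question, since SAP 3.3 declares that change.

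**What to change.** Replace the exclusion sentence in SAP 16.1.2 with: *mITT subjects for whom no post-baseline CS dose is available count as not achieving the 50% reduction, and as 0% reduction in the secondary ANCOVA.* Align SAP 7.3 with it, so that the bar on carrying baseline forward and the WOCF exception read consistently in both places. If the exclusion is kept, list it in SAP 3.3 and add a sensitivity analysis that counts these subjects as non-responders.

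The cost is one SAP sentence plus the matching wording in 7.3, settled before unblinding, and a single-value imputation for a few subjects. No new data are needed. The result may become slightly less or slightly more favourable, depending on the arm. The sample size need not change on this account: power stays above 80% with up to three such subjects in each arm. If two or three fell on IGIV-C alone, it would be 79.8% or 73.8%.

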**16.1.3. PRIMARY ANALYSIS OF PRIMARY EFFICACY VARIABLE**

The primary objective of this study is to test the null hypothesis that the percent of subjects achieving a 50% or greater reduction in CS dose at Week 39 from Baseline in the IGIV-C group is equal to the percent in the Placebo group ( $P_1=P_2$ ). The alternative hypothesis is that the percent of subjects achieving a 50% or greater CS dose reduction in the IGIV-C group is not equal to the percent in the Placebo group ( $P_1 \neq P_2$ ).

The treatment comparison will be analyzed using Cochran-Mantel-Haenszel (CMH) test (Mantel, 1963), adjusted for baseline CS dose level (15-40 mg versus 41-60 mg). The p-value will be based on the general association statistic. The odds ratios for each baseline dose level, the common odds ratio and the Breslow-Day test for homogeneity of the odds ratios will be also summarized.

In the case of sparse events, where at least one of the frequencies is less than 5 in a given cell (i.e., a unique combination of baseline CS dose level, treatment, and the binary response), both unstratified and stratified analyses will be performed using exact methods. For the unstratified analysis, the Fisher's exact test (Agresti, 1992) will be used for treatment comparison. The odds ratio and the exact 95% confidence interval will also be calculated overall and separately for each stratified baseline CS dose level (15-40 mg/day versus 41-60 mg/day). For the stratified analysis, the Zelen's exact test will be used to test homogeneity of odds ratios. The CMH common odds ratio and its exact 95% confidence interval will also be calculated. Finally, an exact test will be used to test the hypothesis of the common odds ratio being 1.

The primary efficacy analysis will be performed for the mITT population.

**16.1.4. SENSITIVITY ANALYSIS OF PRIMARY EFFICACY VARIABLE**

Sensitivity analyses will be performed to assess the robustness of the primary analysis.

Sensitivity to population:

- The primary analysis described in section 16.1.3 will be repeated for the PP population.

Sensitivity to missing data assumptions:

Document: CCI

Author: PPD

Version Number:

Final 2.0

Version Date:

12Apr2019

Template No: CCI

Reference: CCI

Effective Date: 01Apr2016

Copyright © 2009, 2010, 2012, 2016 CCI. All rights reserved.

The contents of this document are confidential and proprietary to CCI. Unauthorized use, disclosure or reproduction is strictly prohibited.

## Analysis Plan

- An analysis of subjects with non-missing daily CS dose at Week 39 will be performed. Subjects with missing daily dose at Week 39 will be excluded. This analysis will be performed on the mITT population using OC data only. The same analyses described in section 16.1.3 will be used.

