3 INVESTIGATIONAL PLAN

3.1 Study Design and Plan

This is a multicenter, randomized, double-blind, placebo-controlled study to evaluate the efficacy and safety of IGIV-C as a CS-sparing agent in CS-dependent MG. Approximately 60 adult subjects will be randomized in this study.

Subjects who have been dependent on systemic corticosteroids for at least the preceding three months and who have received a stable dose of CS for at least one month immediately prior to the Screening visit, will be randomly allocated in a 1:1 ratio into IGIV-C treatment group and Placebo treatment group to receive either IGIV-C or matched Placebo every three weeks in a double-blinded fashion. Randomization will be stratified by baseline CS dose:

- 15 mg 40 mg prednisone equivalent per day
- 41 mg 60 mg prednisone equivalent per day

For those subjects randomized to receive IGIV-C at the Baseline/Week 0 (Visit 1), an initial loading dose of 2 g/kg will be administered at the Baseline Visit (Visit 1). Note that the loading dosage is divided over 2 days as standard infusion time (extensions up to 4 days are allowed for tolerability issues or higher weight, i.e., limit for IGIV-C infusion is no more than 80 g/day [corresponding to 80 kg body weight]). Loading dosage is followed by maintenance doses of 1 g/kg administered every third week until Visit 13 (Week 36). Note that the maintenance dosage is infused in 1 day as standard (extensions are allowed for divided dosage over 2 days for tolerability issues or higher weight, i.e., limit for IGIV-C infusion is no more than 80 g/day [corresponding to 80 kg body weight]). For those subjects randomized to receive Placebo at the Baseline Visit (Visit 1), sterile 0.9% sodium chloride injection, United States Pharmacopeia (USP) or equivalent will be infused in a manner that the blind is maintained. The volumes of Placebo will be equal to the volumes required for an initial loading dose at the Baseline Visit (Visit 1) and subsequent maintenance doses administered every third week until Visit 13 (Week 36).

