3.10 Removal of Subjects

Subjects may withdraw or be withdrawn from the study for the following reasons:

- 1. At their own request or at the request of their legally acceptable representative.
- 2. If, in the investigator's opinion, continuation in the study would be detrimental to the subject's well-being.
- 3. At the specific request of the Sponsor.

Also, subjects must be withdrawn for the following reasons:

- Subjects not meeting the inclusion and exclusion criteria prior to the Baseline (Week 0) Visit based on laboratory results
- Subjects with an occurrence of a concomitant disease or any medical condition which, either because of its severity or duration or necessary change in treatment, contravenes the condition of the study or puts the patient at unnecessary risk or harm
- Subjects with an occurrence of an AE which in the opinion of the investigator and/or subject requires termination of treatment
- If an episode of MG worsening fails to stabilize with the CS dose increase as described in Sections 3.3.3 and 3.3.4 within 6 weeks (by the second subsequent visit), or if another specific episode of MG worsening requires a second dose increase at any time, the subject will be withdrawn from the study. MG crisis requiring hospitalization in accordance with Section 3.3.5 would also be grounds for study discontinuation.
- Subjects who are noncompliant with the protocol per the investigator's discretion
- Pregnancy

In all cases, the reason for withdrawal must be recorded in the eCRF and in the subject's records.

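### The only missing-data sensitivity analysis of the primary endpoint is observed-case, so it cannot show whether the result depends on the LOCF/WOCF imputation

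*SAP*

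**What the plan says.** SAP 16.1.4 lists two sensitivity analyses of the primary endpoint. The first is labelled as sensitivity to population: "The primary analysis described in section 16.1.3 will be repeated for the PP population". The second is the only one labelled as sensitivity to missing-data assumptions. It runs on observed mITT data: "Subjects with missing daily dose at Week 39 will be excluded". SAP 6.4 adds that early-termination data are not mapped to a visit for observed-case analysis, so a subject who leaves before Week 39 contributes nothing to it.

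Protocol 3.3.3 and 3.10 make withdrawal mandatory when MG worsening does not improve within 6 weeks of the dose increase. They do the same for repeat worsening: "if another specific episode of MG worsening requires a second dose increase at any time, the subject will be withdrawn from the study". Hospitalization for MG crisis is also grounds for discontinuation.

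The two documents treat these subjects differently in the primary analysis. Protocol 5.1.3.1 counts anyone who discontinues for MG worsening as a non-responder and applies LOCF to the rest. SAP 7.3 applies WOCF only when a listed discontinuation reason is accompanied by a serious, treatment-emergent MG adverse event with hospitalization or death. Every other discontinuation gets LOCF. SAP 3.3 lists only the move from ITT to mITT as a change from the protocol.

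**The concern.** A missing-data sensitivity analysis should vary the assumption made about the missing subjects and see whether the conclusion moves. Observed-case analysis removes those subjects instead. In this trial some missingness follows from poor outcome by design, because worsening that does not respond, or that recurs, leads to withdrawal. The observed-case estimate can therefore differ from the primary because of who was removed. It can also agree with the primary when the primary depends on the imputation.

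No other planned analysis fills the gap. The per-protocol run repeats the primary analysis, imputation included. The MMRM in SAP 16.3.2.2 covers exploratory change-from-baseline endpoints only. No non-responder, tipping-point or multiple-imputation analysis of the primary endpoint is specified. At stake is whether a reader of the final report can tell how far the responder difference rests on carried-forward doses.

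**Working it through.** **1. Planning figures.** Inputs from protocol 5.1 and 5.2: two-sided alpha 0.05, 80% power, 70% vs 30% response, "a minimum of 24 subjects per treatment group is required", and "Assuming a discontinuation rate in the range of 20%, 60 subjects are planned to be randomized for the study". With pooled variance and no continuity correction:

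n = [1.960·√(2·0.5·0.5) + 0.842·√(0.7·0.3 + 0.3·0.7)]² / 0.4² = (1.386 + 0.545)² / 0.16 = 23.3, so 24 per arm.

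48 / 0.8 = 60. Both figures reproduce. The plan therefore expects about 0.20 × 60 = 12 subjects to discontinue. The documents give neither their reasons nor their split by arm.

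**2. How each planned analysis treats an MG-worsening withdrawal before Week 39.**

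| Analysis | Treatment of that subject |
|---|---|
| Protocol primary | Non-responder |
| SAP primary, serious MG adverse event with hospitalization or death | WOCF, non-responder |
| SAP primary, no such event | LOCF, response depends on last averaged dose |
| SAP per-protocol, if retained | Same as SAP primary |
| SAP observed-case | Removed |

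The third row is not remote. Protocol 4.4.7.3 does not treat variation in MG symptoms as an adverse event unless hospitalization is required, so worsening managed without admission does not generate the event that WOCF requires.

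**3. Can such a subject be an LOCF responder?** Use the taper and increase tables in protocol 3.3.2 and 3.3.3 and the averaging rule in SAP 16.1.1. Take a baseline of 40 mg/day. Steps of 5 mg from Week 9 give 35, 30, 25, 20, 15, 10, and then 5 mg at Week 27. Worsening at Week 30 raises the dose by 15 mg to 20 mg. If there is no improvement by Week 36, the subject is withdrawn. The Week 33 and Week 36 averages are both 20 mg. If no higher dose is recorded afterwards, LOCF gives 1 − 20/40 = 50%, a responder. From 50 mg/day, the taper reaches 10 mg at Week 27, and the increase gives 25 mg, again exactly 50%.

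The limits for an unresponsive first episode at dose d are:
- d ≥ 15: the new dose is at least 35 mg, above half of the 60 mg maximum baseline, so never a response.
- d < 15: the new dose is d + 15, a response only if baseline is at least 2(d + 15), so never with a baseline below 30 mg.

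A second episode can reach lower baselines. From 20 mg/day, a subject who worsens at 5 mg (Week 18), is raised to 20 mg, re-tapers to 10 mg by Week 27 and worsens again at Week 30 has a last average of 10 mg. That is 50%, again if no later increase is recorded.

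**4. Effect of exclusion alone.** Assume 30 per arm, 12 missing, all missing subjects non-responders, and 21/30 vs 9/30 on the full set (40 points, unstratified Fisher p = 0.004). The splits are assumptions.

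| Missing IGIV-C / Placebo | Observed-case | Difference | Fisher p |
|---|---|---|---|
| 0 / 12 | 21/30 vs 9/18 | 20 points | 0.22 |
| 2 / 10 | 21/28 vs 9/20 | 30 points | 0.068 |
| 3 / 9 | 21/27 vs 9/21 | 35 points | 0.018 |
| 6 / 6 | 21/24 vs 9/24 | 50 points | 0.0008 |
| 9 / 3 | 21/21 vs 9/27 | 67 points | <0.001 |

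**5. Effect of one LOCF responder.** The table in step 4 contains no LOCF responder, so a second case is needed. Assume 6 missing per arm and 17 vs 9 observed responders.
- All missing as non-responders: 17/30 vs 9/30, 26.7 points, p = 0.067.
- One missing IGIV-C subject imputed as a responder: 18/30 vs 9/30, 30 points, p = 0.037.
- Observed-case in either situation: 17/24 vs 9/24, 33.3 points, p = 0.041.

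The observed-case result is the same whichever imputation is used. Here it would appear to confirm a primary result that turns on one carried-forward dose.

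**The case against.** The other side has good points. The completer analysis is already in protocol 5.1.3.1, so the SAP implements it and did not introduce it. SAP 7.4 describes a Phase 2 proof-of-concept study. Worsening before withdrawal is captured in time to first MG worsening, and hospitalized worsening has its own exploratory endpoint. Subjects who meet the WOCF criteria cannot be responders. Dose increases, early-termination doses and later unscheduled doses feed LOCF, which narrows the exposure to the cases bounded in step 3. Counting every missing subject as a non-responder is itself an assumption, and it labels someone who leaves at a low dose for an unrelated reason as a failure. All of this stands. It bears on priority, but it does not supply an analysis that varies the imputation.

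A reader might infer three stronger things that the documents do not support:
- That the per-protocol analysis also selects on outcome. SAP 5.4 removes only major violations affecting the primary efficacy data, decided at a blinded review. Withdrawal for worsening follows the protocol and is not in itself a violation. SAP 16.1.4 also offers that run as a check on population, not on missing data.
- That missing Week 39 data are mostly treatment failures. Protocol 3.10 also lists subject or sponsor request, adverse events, concomitant disease, noncompliance and pregnancy, and nothing shows which reason will dominate.
- That observed-case analysis is of no use. It describes completers, including subjects whose first worsening stabilized and who reached Week 39.

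**Conclusion.** The point holds in this form: the single missing-data check for the primary endpoint cannot show whether the result depends on LOCF/WOCF, and the SAP's narrow WOCF rule makes that dependence a practical question. Under the assumptions in step 4, observed-case departs from a 40-point full-set difference by 10 points upward (6/6 missing) or downward (2/10 missing), and the more uneven splits shown give 20 to 67 points. Under those in step 5, one LOCF-imputed responder moves Fisher p from 0.067 to 0.037 while observed-case does not change.

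These figures rest on assumed arm splits, 12 missing of 60 and an unstratified test; the planned test is stratified. They illustrate what can happen and do not predict a direction. The primary test is not shown to be wrong. The gap should be closed, but it does not undermine the design.

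**What to change.** Before unblinding, add to SAP 16.1.4:
- an mITT analysis, tested as in SAP 16.1.3, that counts every subject without an observed Week 39 CS dose as a non-responder. This covers all MG-worsening discontinuations before Week 39, in line with protocol 5.1.3.1, and brings back subjects whom SAP 16.1.2 drops for having no post-baseline dose;
- a tipping-point table by arm, showing how many LOCF-imputed responders would have to be reclassified before the conclusion changes.

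Keep the observed-case analysis and label it supportive or descriptive. The difference between the protocol's non-responder rule and the SAP's WOCF criteria should be reconciled, or recorded in SAP 3.3.

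The cost is one extra table from data already collected, with no change to the primary test. The new estimate may move in either direction, and the text should say that non-responder imputation counts unrelated low-dose dropouts as failures.
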